1.1 Background

1.1.1 Study design

This is a randomized, controlled, evaluator-blinded, multi-center study to evaluate the effectiveness and safety of *Restylane® Kysse* for lip augmentation and correction of perioral rhytids.

Approximately 280 subjects will be randomized in a 2:1 ratio of treatment to control and treated. Approximately 187 subjects will be treated with *Restylane® Kysse* and 93 subjects will receive the control in the lips and perioral rhytids and will be followed for 48-weeks.

Investigator blinding will be accomplished by using a Treating Investigator to administer the treatments and a Blinded Evaluator, to whom randomization and treatment are concealed, to conduct the blinded assessments.

Safety assessments will be performed by non-blinded personnel. Eligible subjects randomized to receive treatment will be injected by the Treating Investigator at Day 1.

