1.6 Safety endpoints

Safety endpoints include:

- (i) Incidence, intensity, duration, and onset of related Adverse Events (AEs) collected during the whole study
- (ii) Incidence, intensity, and duration (defined as number of days with the event) of pre-defined, expected post-treatment events collected using a subject diary for 30 days after each treatment and for each treatment area
- (iii) The safety assessment at all visits, as assessed by a qualified staff member:
 - [REDACTED]
 - [REDACTED]
 - [REDACTED]

Exploratory safety endpoints include:

- (i) Incidence and intensity of related AEs, separated by the following subgroups:
 - Study site
 - Injection volume
 - Fitzpatrick skin types (I-III, IV and V-VI)

[REDACTED]

2 Statistical Methods

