2.5.2 Adverse events

AE terms will be coded using MedDRA dictionary. A treatment-emergent AE (TEAE) is defined as an AE with a start date and time on or after the first study product injection. If relationship to treatment is missing, the event will be conservatively summarized as being related to study product. If intensity is missing, a separate category of missing intensity will be included in the summary table, and no imputation of intensity will be performed. Through the data cleaning process, all attempts will be made to avoid missing values for relationship and intensity.

All AEs will be presented in a by-treatment and by-subject listing, detailing the verbatim term given by the investigator, the preferred term (PT), system organ class (SOC), onset date, end date, intensity, outcome, relationship to study product, relationship to study product injection procedure, action taken with study drug, other action taken, affected treatment area, seriousness and criteria for seriousness. Serious AEs will be presented in a separate listing.

Time to onset of an AE will be derived as the start date minus date of most recent treatment. If the start date is missing, it will be assumed that the AE started on the day of most recent treatment.

Duration of an AE will be derived as the stop date minus the start date + 1. If the start date is missing, it will be assumed that the AE started on the day of most recent treatment. Missing stop date will not be imputed and therefore no duration will be calculated in these cases. Instead, the number of AEs that were ongoing at the end of the study will be given.

An overall summary of AEs will be presented by treatment. The summary will include the total number of events, frequency counts and percentages of subjects with:

- Any TEAE

- Any AE related to product and/or injection procedure
- Unrelated TEAEs
- No TEAEs reported

Summaries of related AEs (including the total number of events, frequency counts and percentages of subjects) will be displayed by treatment and treatment occasion according to the following:

- All AEs by SOC and PT in descending order of frequency (the combined frequency of both treatments)
- All AEs by SOC, PT, and maximum intensity (mild, moderate, or severe)
- All AEs by SOC, PT, and action taken (none, medical treatment, non-pharmacological treatment, subject withdrawn)

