For related AEs, the number of days to onset and duration of event will be summarized by SOC and PT, using mean, SD, minimum, maximum, and median statistics.

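### Setting a missing AE start date to the day of the most recent treatment gives that event an onset of 0 days, usually lengthens its duration, and leaves unclear which treatment is meant

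*SAP*

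**What the plan says.** All of the relevant rules are in the SAP.

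- Section 1.6 lists as its first safety endpoint: "Incidence, intensity, duration, and onset of related Adverse Events (AEs) collected during the whole study".
- Section 2.5.2 defines onset: "Time to onset of an AE will be derived as the start date minus date of most recent treatment". It defines duration: "Duration of an AE will be derived as the stop date minus the start date + 1".
- Each definition is followed by the same rule for an unknown start: "If the start date is missing, it will be assumed that the AE started on the day of most recent treatment".
- An unknown stop date is treated differently: "Missing stop date will not be imputed and therefore no duration will be calculated in these cases". The SAP gives the number of AEs still ongoing at study end instead. Missing intensity is likewise not imputed and gets its own category.
- The derived values are then reported: "For related AEs, the number of days to onset and duration of event will be summarized by SOC and PT", as mean, SD, minimum, maximum and median.
- Section 2.5.1 names three points at which product may be injected: initial treatment, touch-up and a Week 48 retreatment.

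The SAP gives no count or flag of assumed start dates and no summary without them. Its sentence on avoiding missing values through data cleaning covers relationship and intensity only.

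**The concern.** The rule fills an unknown date with one particular value and then summarizes the result as if it had been observed. The assumed onset is the smallest value possible for an event after treatment. The same assumption makes the event as long as its stop date allows. Both errors enter summaries of a stated endpoint, and they act most on the minimum onset and the maximum duration, each of which a single event can set. In a study whose subjects "will be followed for 48-weeks", onset can truly lie far from day 0.

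There is also a gap in the definition. The most recent treatment is normally found by looking back from the AE start. When the start is what is missing, the SAP does not say from which date to look back. Two programmers could choose different treatments for the same event.

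**Working it through.** The SAP gives no figure to reproduce here, so the check applies its own formulas to events with known true dates.

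**Effect on one event.** Let treatment be on day 0, true onset on day L and true duration D. The stop date is then day L + D − 1.

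- True values: onset = L − 0 = L; duration = (L + D − 1) − L + 1 = D.
- With the start set to day 0: onset = 0 − 0 = 0; duration = (L + D − 1) − 0 + 1 = L + D.

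Onset therefore shifts by −L days and duration by +L days. For an assumed 10-day event (D = 10):

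| True onset (day) | Derived onset | Derived duration |
|---|---|---|
| 0 | 0 | 10 |
| 7 | 0 | 17 |
| 30 | 0 | 40 |
| 60 | 0 | 70 |
| 180 | 0 | 190 |

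An event that truly began on the treatment day is unchanged. If the stop date is also missing, no duration is calculated and only onset is affected.

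**Effect on a summary.** Assume a preferred term with ten related AEs, all with true onset on day 60 and true duration 10 days. The number with a missing start date is not in the documents, so it is varied.

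| Missing starts | Mean onset | Median onset | Min onset | Mean duration | Median duration | Max duration |
|---|---|---|---|---|---|---|
| 0 | 60 | 60 | 60 | 10 | 10 | 10 |
| 1 | (9×60 + 0)/10 = 54 | 60 | 0 | (9×10 + 70)/10 = 16 | 10 | 70 |
| 2 | (8×60 + 0)/10 = 48 | 60 | 0 | (8×10 + 2×70)/10 = 22 | 10 | 70 |
| 5 | (5×60 + 0)/10 = 30 | 30 | 0 | (5×10 + 5×70)/10 = 40 | 40 | 70 |

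One missing date is enough to change the minimum and maximum. The medians hold with one or two missing in ten and move only when missing dates are common. Ten identical late events make the contrast sharper than a mixed set would.

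**Which treatment is the most recent.** Take an event truly on days 20 to 40, so that its duration is 40 − 20 + 1 = 21 days. Assume treatments on days 0, 28 and 336; the last is 48 × 7, and the touch-up day is an assumption. With the start date missing:

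- looking back to the initial treatment: 40 − 0 + 1 = 41 days;
- looking back to the touch-up: 40 − 28 + 1 = 13 days;
- looking back to the retreatment: 40 − 336 + 1 = −295 days.

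The derived onset is 0 in all three cases. Duration can thus be too long, too short or impossible. The last case arises only if the look-back starts from a date after the retreatment, such as a late report date. The SAP neither states that reading nor excludes it.

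**The case against.** The strongest reply is that this is an explicit convention, fixed in advance and applied alike to both arms, in a descriptive analysis on which no test or decision depends. The rate of missing start dates is unknown. The supplied protocol's AE form asks for a start date (section 8.2.3), so few may be missing. Leaving events out has its own cost. All of this stands and limits the weight of the point. It does not make the derived onset or duration right for an affected event.

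A reader might infer several stronger things that the documents do not support.

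- *The rule hides delayed reactions.* All AEs appear in by-subject listings with onset and end dates. Incidence and intensity do not use the onset value, and diary symptoms are counted as days with the event. None of these is shown to be affected.
- *Late events lose their start dates more often.* This is plausible, but nothing in the documents supports it.
- *The rule discards a known month or year.* The SAP speaks only of a missing start date and does not say that a partial date counts as missing.
- *The rule is a cautious way to classify AEs as treatment-emergent that has spilled over into the summaries.* The SAP's treatment-emergent definition has no rule for missing dates; the assumption appears only under onset and duration.
- *Events are placed in the wrong treatment occasion.* Section 2.5.1 gives the occasions as initial treatment or retreatment, so confusing the first injection with the touch-up changes nothing. Only a Week 48 retreatment could matter, and the SAP does not say that the assumed date decides the occasion.

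**Conclusion.** The point holds as a small, definite flaw. For each related AE with a missing start date, derived onset is exactly 0 days. Where the stop date is known and the event began after the treatment used, derived duration is too long by the true time to onset. This follows from the SAP's formulas without any assumption about how often dates are missing.

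The effect on the reported tables does depend on that rate. With few missing dates it falls on the mean, minimum and maximum and hardly on the median; with none there is no effect. The figures for ten events are illustrations, not estimates.

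Separately, the reference treatment is undefined when the start is unknown and there has been more than one treatment. That gap should be closed whatever the rate.

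The conclusion concerns the SAP as written. The SAP describes a randomized study of about 280 subjects, whereas the supplied protocol describes an open-label study of 50 to 60. The rule therefore cannot be assumed to govern the protocol's study, and the data-collection safeguards of the SAP's own study cannot be judged.

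**What to change.** Amend SAP section 2.5.2 in three places.

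1. In the onset and duration summaries, leave out related AEs whose start date is fully missing, and report how many there are beside each summary. The SAP already does this in kind for missing stop dates.
2. Define the most recent treatment as the last one on or before the AE start or, when the start is unknown, the last one on or before the stop date. An assumed start then cannot fall after the stop date.
3. If the assumed date is wanted for classifying an AE as treatment-emergent, say so in that definition, where no such rule now stands.

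The cost is two or three sentences and minor programming. The downside is that a few events contribute no onset or duration value. If the chance of a missing date is related to onset, the remaining events are not fully representative, which is why the count must be shown.

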8.2.6 Follow-up of unresolved events ongoing at termination of the study

All serious as well as non-serious AEs with a causal relationship to the study product or treatment procedure and ongoing at study end, shall be followed up after the subject's participation in the study is over. Such events shall be followed up after the last study visit until resolved, assessed as chronic or stable, or for three months. Final outcome after the end of the study shall be reported on AE follow-up form.

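### AE duration in SAP 2.5.2 is summarised over resolved events only, so it is understated wherever related events are still open at study end or withdrawal

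*SAP*

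**What the plan says.** SAP 1.6 lists as safety endpoint (i): "Incidence, intensity, duration, and onset of related Adverse Events (AEs) collected during the whole study".

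SAP 2.5.2 gives the derivation: "Duration of an AE will be derived as the stop date minus the start date + 1". For events with no stop date: "Missing stop date will not be imputed and therefore no duration will be calculated in these cases". The next sentence adds: "Instead, the number of AEs that were ongoing at the end of the study will be given". For a missing start date the rule differs: "If the start date is missing, it will be assumed that the AE started on the day of most recent treatment".

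The section closes with the summary for related AEs: "duration of event will be summarized by SOC and PT, using mean, SD, minimum, maximum, and median statistics". It also plans a listing of every AE by treatment and subject, with onset date, end date and outcome.

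The visible text plans no censored-data summary, no minimum duration for open events and no sensitivity analysis. It does not say that the ongoing count will be broken down by SOC and PT or placed beside the duration table.

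**The concern.** A stop date is usually absent because the event had not resolved when the subject was last seen. Leaving such events out means summarising duration given that the event ended within observation. That is a different quantity from duration, and a smaller one.

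For a filler, persistent events are the ones a reader of a duration table most wants to see. A SOC/PT row could show a short mean and a modest maximum while several events under that term remain open. The count of ongoing events is tied to the end of the study, so events open when a subject withdraws may appear in neither the statistics nor the count.

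**Working it through.** **Inputs.** Follow-up comes from SAP 1.1.1: subjects "will be followed for 48-weeks", or 48 × 7 = 336 days. The documents state no AE duration or ongoing rate, so there is no planned figure to reproduce, and every duration distribution below is an assumption.

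**Direction.** Let D be the true duration and C the time from onset to last observation. The SAP summarises D given D ≤ C. If C is independent of D, then E[D | D ≤ C] ≤ E[D], strictly once any event is cut off. The maximum over resolved events cannot exceed the maximum over all events.

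**Formulas.** For exponential D with mean m and a fixed window c:
- P(resolved) = 1 − e^(−c/m)
- E[D; resolved] = m − (c + m)e^(−c/m)

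For C uniform on (a, b):
- P(resolved) = 1 − [m/(b − a)] × [e^(−a/m) − e^(−b/m)]
- E[D; resolved] = m − [m/(b − a)] × [(a + 2m)e^(−a/m) − (b + 2m)e^(−b/m)]

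The reported mean is E[D; resolved] / P(resolved). Medians were solved numerically from the corresponding distribution functions.

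**Case 1: early onset.**
- Short reactions, lognormal with median 7 days and log-SD 0.8: essentially none are open at day 336. The mean stays at 7 × e^0.32 = 9.6 days and the median at 7.0.
- Longer events, m = 60 and onset on days 0–3, so c ≈ 334.5: e^(−334.5/60) = 0.0038. The reported mean is (60 − 394.5 × 0.00379)/0.9962 = 58.7 against 60, about 2% low.

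**Case 2: onset spread over follow-up.** m = 30, C uniform on 1 to 336 days.
- P(resolved) = 1 − (30/335)(0.9672 − 0.0000) = 0.913, so about 9% are open.
- E[D; resolved] = 30 − (30/335)(61 × 0.9672 − 396 × 0.000014) = 24.7.
- Reported mean 24.72/0.9134 = 27.1 against 30.0, about 10% low. Reported median 18.9 against 20.8, about 9% low.

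**Case 3: a persistent minority.** 90% short reactions as in Case 1; 10% exponential with m = 180 and onset spread over follow-up.
- Long events: P(resolved) = 1 − (180/335)(0.9945 − 0.1546) = 0.549. E[D; resolved] = 180 − (180/335)(361 × 0.9945 − 696 × 0.1546) = 44.9.
- Share of all events open: 0.10 × 0.451 = 4.5%.
- Reported mean (0.9 × 9.64 + 0.1 × 44.93)/(0.9 + 0.0549) = 13.8. True mean 0.9 × 9.64 + 0.1 × 180 = 26.7. The reported mean is about 48% low.
- Reported median 7.4 against 7.8, about 5% low.
- In a simulation of 400,000 events under the same assumptions, the Kaplan-Meier median with open events censored was 7.8, equal to the true value.

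So the mean can be badly wrong when fewer than 5% of events are open, while the median moves little.

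**The case against.** The best defence is that nothing is hidden. The SAP counts ongoing events and lists each AE with its dates and outcome, so unresolved events can be found. The summary is descriptive and carries no inference. Diary symptoms, the likely bulk of injection reactions, are summarised as number of days with the event and are outside this rule. With 48 weeks of follow-up, most early reactions will have ended. The missing-start-date rule also works the other way, since it can only lengthen a later-starting event. All of this stands and limits the size of the point. It does not make the tabulated mean, median or maximum describe the duration of all related events.

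Four stronger readings are tempting, and the documents do not support them.

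- **That the rule removes exactly the longest events.** It removes events without a stop date. A long event that resolves is kept, and a short one that begins late can be dropped. In a simulation of Case 2, 12% of the excluded events were truly shorter than the median resolved event.
- **That the bias should be judged over a follow-up of about eight weeks.** Week 8 in the SAP is the primary efficacy time point. AEs are collected throughout the study. The eight-week final visit belongs to the protocol, which describes a separate open-label study.
- **That the plan discards outcome dates it already holds.** Protocol 8.2.6 does follow related ongoing events: "Such events shall be followed up after the last study visit until resolved, assessed as chronic or stable, or for three months". But that is the open-label study's protocol, and nothing visible shows that the randomized trial in the SAP collects the same.
- **That a comparison between arms is distorted.** The SAP describes duration by SOC and PT and states no between-arm contrast or test of it.

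**Conclusion.** The point holds as a minor one. The SAP's duration endpoint is understated wherever related events are open at study end or withdrawal, and the planned disclosures do not correct it. The direction follows from the rule, provided the time available for observation is unrelated to an event's duration. The size cannot be read from the documents. Under the assumptions above it runs from nil for short early reactions, through about 10% on mean and median for month-long events with spread onset, to about half on the mean and 5% on the median with a persistent minority. Events after the Week 48 retreatment mentioned in SAP 2.5.1 may be more exposed, but the visible text does not say how long subjects are followed after it, so no figure is offered. No efficacy or primary conclusion is affected.

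**What to change.** Amend SAP 2.5.2 so that an event without a stop date is treated as right-censored at the subject's last contact. Report the Kaplan-Meier median and quartiles of duration by SOC and PT where counts allow.

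Where they do not, keep the existing statistics but label them as resolved events only. Beside them, by SOC and PT, show the number unresolved, including those open at withdrawal, and their observed days marked as minimum durations.

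The cost is a change of SAP wording and slightly more programming, using onset and last-contact dates already collected. The downside is that medians may be inestimable for rare terms, which is why the second form of display is needed. Censoring at last contact also assumes that leaving the study is unrelated to how long the event would have lasted; the SAP should say so.

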2.5.3 Pre-defined, expected, post-treatment symptoms

Frequency counts and percentages of subjects reporting each pre-defined, expected, post-treatment symptoms (i.e. bruising, redness, tenderness, swelling, pain, itching, lumps/bumps, discoloration, and other symptoms), as collected in the 30 day diary after each treatment, will be presented in total and by maximum severity, for each treatment area separately.

Number of days with the event will also be summarized using mean, SD, min, max, and median.

2.5.4 Safety assessment

will be presented with frequency counts and percentages of subjects classified as “Normal” or “Abnormal” by visit.

Urine pregnancy test results will be presented in a by-subject listing.

2.5.5 Exploratory safety endpoints

- Related AEs by SOC, PT and maximum intensity will be separately summarized for the following subgroups:
 - Study site
 - Injection volume
 - Fitzpatrick skin types (I-III, IV and V-VI)
- [REDACTED]

2.6 Interim Analysis

There is no interim analysis planned.

2.7 Determination of Sample Size

Accounting for approximately 15% drop-outs and non-evaluable subjects due to protocol deviations at week 8, a total of approximately 280 subjects will be randomized in the study. It is expected that the number of randomized subjects will be similar across the study sites.

2.8 Changes

3 Reference List

4
